7.2.5 Sponsor Responsibility for Reporting Adverse Events

All Adverse Events will be reported to regulatory authorities, IRB/IECs and investigators in accordance with all applicable global laws and regulations, i.e., per ICH Topic E6 (R1) Guidelines for Good Clinical Practice.

8.0 STATISTICAL ANALYSIS PLAN

This section outlines the statistical analysis strategy and procedures for the study. Changes to analyses made after the protocol has been finalized, but prior to unblinding, will be documented in a supplemental SAP (sSAP) and referenced in the Clinical Study Report (CSR) for the study. Post hoc exploratory analyses will be clearly identified in the CSR.

8.1 Statistical Analysis Plan Summary

Key elements of the statistical analysis plan are summarized below; the comprehensive plan is provided in Sections 8.2 through 8.12.

Study Design Overview	Phase 1/1b Trial MK-1966 in combination with SD-101 in Subjects With Advanced Malignancies. A 3+3 design in part A to identify preliminary MTD; TPI design for dose confirmation on two malignancies (melanoma and squamous cell cancer of head and neck), followed by approximately 24 weeks follow-up as an expansion cohort on both malignancies.
Analysis Populations	Safety: All Subjects as Treated (ASaT) PK and target engagement (secondary): Per-Protocol (PP) Efficacy (exploratory): Full Analysis Set (FAS)
Primary Endpoint(s)	Safety: DLT
Key Secondary Endpoints	PK parameters of MK-1966 in combination with SD-101 Target engagement for MK-1966
Statistical Methods for Key Efficacy/Immunogenicity/ Pharmacokinetic Analyses	Serum concentrations of MK-1966 will be summarized by planned visit and time for each dose separately; PK parameters will be summarized by dose. Target engagement will be summarized by planned visit and time for each dose separately.
Treatment Assignment	Subjects are allocated to increasing doses of MK-1966 co-administered with SD-101 without randomization; the study is open-label
Statistical Methods for Key Safety Analyses	DLT and adverse experiences will be summarized as counts and frequencies for the dose level with at least three subjects. The estimate of the DLT rate among subjects treated with the RPTD and the 80% Bayesian probability interval for the estimate will be provided.
Interim Analyses	Study has no interim analyses
Multiplicity	No multiplicity adjustment is planned in this Phase I/Ib study.
Sample Size and Power	The sample size of the dose escalation (Part A), and dose confirmation/expansion (Parts B and C) depends on the observed DLT profiles of MK-1966 co-administered with SD-101. The sample size of approximately 64 subjects will be used for study planning purposes.

8.2 Responsibility for Analyses/In-House Blinding

The statistical analysis of the data obtained from this study will be the responsibility of the Clinical Biostatistics department of the SPONSOR.

This trial is conducted as an open-label trial, i.e., subjects, investigators, and SPONSOR personnel will be aware of subject treatment assignments after each subject is enrolled and treatment is assigned. Allocation to treatment will not be randomized.

The database will be locked for analysis approximately 24 weeks after the enrollment of the last subject.

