- g. MK-1966 Pharmacokinetics (PK) samples will be collected more frequently in Cycles 1-3. On Days 1, 22 and 43 -collect predose, at the end of infusion and 2h after the start of the infusion (+10 minutes). On Day1 of Cycles 4-8 collect PK samples predose. Also collect PK Samples on Days 2, 3, 8, 15, 29, 36, 50, 57, at the treatment discontinuation, and Safety Follow-up visit (30 days post end of treatment).
- h. Blood samples for IL-10 Pharmacodynamics (PD) will be drawn at Screening and at times that match PK sampling in footnote “i” above.
- i. Unilateral bone marrow biopsy and aspirate will be performed at Screening if not previously performed or if performed more than 90 days previously with negative results. The bone marrow biopsy will be performed to confirm a CR if the subject was initially positive or if it is clinically indicated by new abnormalities in the peripheral blood counts or blood smear (section 4.2.3.5)
- j. When SD-101 and MK-1966 are scheduled on the same day, SD-101 will be administered first. MK-1966 will be administered at least 30 minutes after the SD-101 injection.
- k. These samples may be performed up to 72 hours prior to dosing. However, in Cycle 1 on Day 1, samples are to be drawn prior to dosing and should be used as the subject's baseline (not screening) values.
- l. Include HCV, RNA (qualitative) or Hepatitis C antibody, HBsAg, and HIV type 1 and type 2 (e.g., HIV-1/-2 antibody screening test and evaluation of HIV viral load as needed).
- m. Patients who discontinue from treatment or have completed post treatment follow up should be contacted every three months to monitor overall survival (for up to 2 years from last dose of study drug or until the sites are notified by the Sponsor that the survival follow up is no longer required).
- n. The Day 9 visit must be 24 hours (+/- 4 hours) after the Day 8 visit.
- o. Sample(s) and/or procedures will be collected prior to dosing and when applicable as outlined in the Procedures Manual.
- p. Record all AEs occurring from signing of informed consent until 30 days after the last dose of MK-1966 and SD-101. Report all SAEs occurring up to 30 days after the last dose of treatment
- q. Dosing with MK-1966 and/or SD-101 will occur within the timeframes outlined in section 5.2.5. and/or the Procedures Manual.
- r. After the SD-101 is injected, the injection site should be observed every 15 minutes for at least 90 minutes.

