- s. End of Cycle 8 is defined as 21 days post Cycle 8, Day 1 or Day 168.
- t. The Cycle 2 (or Day 22) and End of Treatment tumor samples are optional.

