7.1.5.2 Treatment Period

Visit requirements are outlined in Section 6.0 - Trial Flow Chart. Specific procedure-related details are provided above in Section 7.1 - Trial Procedures.

After a screening phase of up to 28 days, eligible subject(s) will be assigned a dose levels by the sponsor. MK-1966 and SD- 101 treatment will be administered as outlined in Section 5.2 for 8 cycles (approximately 24 weeks) of study medication in Part A, B, C, or administrative reasons requiring cessation of treatment. After the end of treatment (EOT), each subject will be followed for 30 days. Serious adverse events (SAEs) will be collected for 30 days after EOT.

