7.1.5.2.1 Safety Follow-up Visit

The mandatory Safety Follow-Up Visit should be conducted approximately 30 days after the last dose of trial treatment or before the initiation of a new antineoplastic treatment, whichever comes first. Subjects with an AE of Grade >1 will be further followed until the resolution of the AE to Grade 0-1 or until beginning of a new antineoplastic therapy, whichever occurs first.

Visit requirements are outlined in Section 6.0 - Trial Flow Chart.

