All adverse events that occur after the consent form is signed but before treatment allocation/randomization must be reported by the investigator if they cause the subject to be excluded from the trial, or are the result of a protocol-specified intervention, including but not limited to washout or discontinuation of usual therapy, diet, placebo treatment or a procedure. From the time of treatment allocation/randomization through 14 days following cessation of treatment, all adverse events must be reported by the investigator. Such events will be recorded at each examination on the Adverse Event case report forms/worksheets. The reporting timeframe for adverse events meeting any serious criteria is described in section 7.2.3.1. The investigator will make every attempt to follow all subjects with non-serious adverse events for outcome.

Electronic reporting procedures can be found in the Electronic Data Capture (EDC) data entry guidelines. Paper reporting procedures can be found in the Investigator Trial File Binder (or equivalent).

Adverse events will not be collected for subjects during the pre-screening period (for determination of archival tissue status) as long as that subject has not undergone any protocol-specified procedure or intervention. If the subject requires a blood draw, fresh tumor biopsy etc., the subject is first required to provide consent to the main study and AEs will be captured according to guidelines for standard AE reporting.

7.2.1 Definition of an Overdose for This Protocol and Reporting of Overdose to the Sponsor

For purposes of this trial, an overdose will be defined as any dose exceeding (by > 50%) the prescribed dose for SD-101 and/or MK-1966. No specific information is available on the treatment of overdose of MK-1966. In the event of overdose, MK-1966 should be discontinued and the subject should be observed closely for signs of toxicity. Appropriate supportive treatment should be provided if clinically indicated.

If an adverse event(s) is associated with ("results from") the overdose of Sponsor's product or vaccine, the adverse event(s) is reported as a serious adverse event, even if no other seriousness criteria are met.

If a dose of Sponsor's product or vaccine meeting the protocol definition of overdose is taken without any associated clinical symptoms or abnormal laboratory results, the overdose is MK-1966-001-03 Final Protocol

9-Feb-2017

Confidential

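### Section 8.2 sets the database lock at the last subject's end of Cycle 8, ahead of the mandatory Safety Follow-up Visit for up to 4-5 late-enrolled completers

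*Combined protocol and SAP*

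**What the plan says.** **Lock.** SAP Section 8.2: "The database will be locked for analysis approximately 24 weeks after the enrollment of the last subject". Section 8.6.3.3 plans no interim analysis, and no later lock or update is described.

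**End of treatment.** Flow chart (Section 6.0), footnote s: "End of Cycle 8 is defined as 21 days post Cycle 8, Day 1 or Day 168".

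**Safety Follow-up Visit.** Section 7.1.5.2.1 makes this visit mandatory, at about "30 days after the last dose of trial treatment or before the initiation of a new antineoplastic treatment, whichever comes first". The flow chart uses a different anchor. Its column heading counts 30 days from the end of the treatment period, and footnote g schedules PK samples "at the treatment discontinuation, and Safety Follow-up visit (30 days post end of treatment"). Under footnote h, IL-10 samples "will be drawn at Screening and at times that match PK sampling". As read from the flow chart, adverse event review and an anti-drug antibody sample also belong to this visit.

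**Adverse event windows.** Footnote p: "Record all AEs occurring from signing of informed consent until 30 days after the last dose of MK-1966 and SD-101". Section 7.1.5.2: "Serious adverse events (SAEs) will be collected for 30 days after EOT". Section 7.2, however, says: "From the time of treatment allocation/randomization through 14 days following cessation of treatment, all adverse events must be reported by the investigator". Section 7.2.3.1 uses the same 14 days for serious events.

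**Study duration.** Section 8.6.3.5 counts from first dose to the end of the last subject's treatment period. It gives 1.8 years for both 52 + 24 weeks and 64 + 24 weeks. The Trial Summary also gives 1.8 years, but counts from first consent to the last visit or call.

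**The concern.** The lock falls when the last subject finishes Cycle 8, so anything the protocol requires after that point is missing for the latest enrollees. Safety and tolerability is the primary objective, and Section 8.6.2 reports percentages of RPTD subjects with any, drug-related and serious adverse events. If the top dose is confirmed without de-escalation, as in Scenario 2, the late Part B and C subjects are all in that summary.

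The weeks after the last dose are not a formality for a slowly cleared antibody. Table 1's predicted human values give a half-life of roughly ln 2 × 78 / 2.4 = 22.5 days (one-compartment approximation). PK and target engagement are secondary endpoints, and the visit carries their last scheduled samples.

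**Working it through.** **Inputs.** Lock at 24 weeks = 168 days after last enrolment (8.2). Eight three-week cycles (Table 5). One enrolment per week (8.6.3.5). Visit window of 3 days either side (as read from the flow chart). Enrolment is taken as Day 1, since Section 5.2 starts treatment on or near the day of allocation.

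**The plan's own figure.** 8 × 21 = 168 days = 24.0 weeks, so the lock coincides with end of Cycle 8. Counting 21 days from Cycle 8 Day 1 strictly gives Day 169; the one-day difference changes no count below.

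**Visit day for an on-schedule completer.**
- Cycle 8 Day 1 = 1 + 7 × 21 = Day 148.
- Last-dose anchor: 148 + 30 = Day 178, which is 9 to 10 days after lock.
- End-of-treatment anchor: 168 + 30 = Day 198, which is 29 to 30 days after lock.

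**Subjects lacking the visit.** A subject enrolled k weeks before the last has 168 + 7k days elapsed at lock. The visit on day V is missing if 168 + 7k < V − 1, that is, 7k < V − 169.

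| Anchor | 3 days early | On time | 3 days late |
|---|---|---|---|
| Day 178 | 7k < 6: 1 | 7k < 9: 2 | 7k < 12: 2 |
| Day 198 | 7k < 26: 4 | 7k < 29: 5 | 7k < 32: 5 |

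If the lock slips to 26 weeks (182 days), the Day 178 count is 0 and the Day 198 count is 3. At 29 weeks (203 days) both are 0.

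Of the 40 Part B and C subjects, 1-2 is 2.5%-5% and 4-5 is 10%-12.5%. The documents give no completion rate. If half of the late subjects complete eight cycles without new therapy (assumption), the counts fall to about 0.5-1 and 2-2.5. If each late subject has one 2-week interruption (assumption, from Section 5.2.5), they rise to 3-4 and 6-7.

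**Adverse event windows still open at lock (one enrolment per week).**
- 14 days from last dose (Day 162): 0 subjects.
- 14 days from end of treatment (Day 182): 2.
- 30 days from last dose (Day 178): 2.
- 30 days from end of treatment (Day 198): 5.

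**Lock needed to include the last visit, 3 days late.** Day 181: 180 / 7 = 25.7 weeks. Day 201: 200 / 7 = 28.6 weeks.

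**Durations.**
- Scenario 1: 76 × 7 / 365.25 = 1.46 years.
- Scenario 2: 88 × 7 / 365.25 = 1.69 years. Neither is 1.8 on the definition in 8.6.3.5.
- Trial Summary, Scenario 2 from first consent: 28 days of screening + 616 + 10 days to the Day 178 visit = 654 days = 1.79 years, without survival calls.

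**The case against.** - **The lock is only approximate.** Two weeks of slippage removes the gap on the last-dose anchor, so the lower bound is 0. This stands. It does not stretch easily to the 30-day gap on the flow chart's anchor.
- **Other documents may settle it.** Section 10.6 leaves data management procedures to a separate document, and exploratory endpoints and efficacy methods are in a supplemental SAP. Data collection could continue after a lock for analysis. That is possible, but Section 8.2 does not say so or point there.
- **Loss of serious adverse event data is not certain.** A reader might infer that part of the serious event window is definitely cut off. The documents do not support that: the 14-day rule counted from last dose closes on Day 162, before lock. Nor is expedited reporting affected. Serious events within the window in Section 7.2.3.1 must reach the Sponsor within 24 hours whenever the lock occurs.
- **Unconfirmed progression at Week 24 cannot be counted.** A reader might infer that a fixed number of subjects would await a confirmation scan at lock. Footnote e ends imaging at discontinuation or End of Treatment, while Section 7.1.2.6.3.1 continues it every 12 weeks until confirmed progression. Section 4.2.3.6 sets only a minimum of 4 weeks for the repeat scan and frames it around continuing treatment. No number follows.
- **The Trial Summary's 1.8 years can be reproduced** for Scenario 2, so only the figures in 8.6.3.5 are mismatched.

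**Conclusion.** The point holds as a minor one. As written, the lock precedes the mandatory Safety Follow-up Visit of on-schedule completers who start no new therapy. The number affected is 0-2 on the last-dose anchor and up to 4-5 on the end-of-treatment anchor. These counts assume one enrolment per week and no dosing delays; early discontinuation or new therapy lowers them, and interruptions raise them. Whether adverse event data are also incomplete depends on which window governs, and the text does not settle that.

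The 21-day DLT endpoint, the MTD and the RPTD are untouched. A reader might go further and infer biased PK, target-engagement or efficacy results. The documents do not show this: PK sampling is densest in Cycles 1-3, PK and target engagement are summarized descriptively by visit or dose, and efficacy is exploratory.

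**What to change.** 1. Reword Section 8.2 so that the lock follows the last treated subject's Safety Follow-up Visit plus data cleaning. Before cleaning and any dosing interruption, this is about 26 weeks after last enrolment on the last-dose anchor or about 29 weeks on the end-of-treatment anchor. Do not tie the lock to confirmation scans unless the imaging passages are reconciled to require them after Week 24.
2. Reconcile the 14-day windows (7.2, 7.2.3.1) with the 30-day windows (footnote p, 7.1.5.2), the two anchors for the visit, and footnote e with Section 7.1.2.6.3.1.
3. In Section 8.6.3.5, restate 52 + 24 weeks as about 1.5 years and 64 + 24 weeks as about 1.7 years. The Trial Summary should say that its 1.8 years corresponds to Scenario 2, from first consent to last visit, without survival calls.

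The cost is a lock about 2 weeks (26 − 24) to 5 weeks (29 − 24) later, plus cleaning time and any interruption, and some wording changes. No visits or samples are added.

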8.3 Hypotheses/Estimation

Objectives and hypotheses of the study are stated in Section 3.0.

8.4 Analysis Endpoints

Efficacy and safety endpoints are listed below, followed by the descriptions of the derivations of selected endpoints.

8.4.1 Efficacy/Immunogenicity/Pharmacokinetics Endpoints

Efficacy endpoints and their definitions are presented in Section 8.4.3.

8.4.2 Safety Endpoints

The primary safety endpoint is DLT. Safety will be monitored by cumulative data reviews throughout the trial. The toxicities and grades experienced by subjects who have received study treatment, including adverse events (AEs) and serious adverse events (SAEs) will be summarized. Other safety measures evaluated in all parts of the study include laboratory safety assessments, ECGs, vital signs, and physical examinations.

8.4.3 Derivations of Efficacy/Immunogenicity/Pharmacokinetics Endpoints

Secondary PK endpoints and exploratory efficacy endpoints and their definitions are presented below.

PK endpoints- serum concentrations of MK-1966 and derived PK parameters.

Target engagement endpoints – Total IL-10, free IL-10, to be used in descriptive analyses

Exploratory endpoints

Exploratory endpoints are documented in a supplemental SAP (sSAP). Additional supportive analyses of these endpoints based on irRECIST or Cheson criteria and, if needed, central review might be conducted.

8.4.4 Derivations of Safety Endpoints

Description of safety measures is provided in Section 7.

8.5 Analysis Populations

8.5.1 Safety Analysis Populations

The All-Patients-as-Treated (APaT) population will be used for the analysis of safety data in this study. The APaT population consists of all subjects who received at least one dose of study treatment. In case of treatment administration errors, subjects will be analyzed according to the treatment they actually received. For DLT evaluation, APaT subjects that were observed for safety for 21 days after the first dose of assigned treatment or experienced a DLT prior to 21 days after the first dose of assigned treatment will be used.

At least one laboratory or vital sign measurement obtained subsequent to at least one dose of study treatment is required for inclusion in the analysis of each specific parameter. To assess change from baseline, a baseline measurement is also required.

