5.2.1.2.2 Dose Confirmation/Expansion

The objective of dose confirmation in Part B and C is to refine the estimate of the MTD based on TPI design [1] with target toxicity rate $\leq 30\%$. Dose confirmation involves the expansion of at least 1 dose level studied in the dose escalation stage of the study.

Dose confirmation will begin with expansion of the preliminary MTD/MAD identified in the dose escalation stage described in Section 5.2.1.2.1. The dose confirmation part will continue until 20 subjects are studied at the selected dose (combined from dose escalation and dose confirmation) with ≤ 7 of 20 subjects experiencing a DLT. As subjects become evaluable for DLT assessment, the number of subjects who are evaluable for DLT versus the number of subjects who developed a DLT will be continuously assessed. De-escalation and escalation to eligible doses will occur during dose confirmation as shown in [Table 6](#). Escalation or reduction of dose for either agent will be to the next higher or lower dose on MK-1966 being examined in this study, while keeping SD-101 dose fixed. However dose escalation will not exceed 700 mg of MK-1966 or 4 mg of SD-101. Likewise a cohort dose will not be reduced below 70 mg of MK-1966 or 1 mg of SD-101.

Table 6 Dose Confirmation Rules

Number of toxicities	Number of subjects treated at current dose																		
	4	5	6	7	8	9	10	11	12	13	14	15	16	17	18	19	20		
0	S	E	E	E	E	E	E	E	E	E	E	E	E	E	E	E	E	E	
1	S	S	S	S	S	E	E	E	E	E	E	E	E	E	E	E	E	E	
2	D	S	S	S	S	S	S	S	S	S	E	E	E	E	E	E	E	E	
3	DU	D	D	S	S	S	S	S	S	S	S	S	S	S	S	S	S	E	
4	DU	DU	DU	D	D	S	S	S	S	S	S	S	S	S	S	S	S	S	
5		DU	DU	DU	DU	DU	D	D	S	S	S	S	S	S	S	S	S	S	
6			DU	DU	DU	DU	DU	DU	D	D	D	S	S	S	S	S	S	S	
7				DU	DU	DU	DU	DU	DU	D	D	D	D	D	S	S	S	S	
8					DU	D	D	D	D	D	D								
9						DU	D	D											
10							DU												
11								DU											
12									DU										
13										DU									
14											DU								
15												DU							
16													DU	DU	DU	DU	DU	DU	
17														DU	DU	DU	DU	DU	
18															DU	DU	DU	DU	
19																DU	DU	DU	
20																	DU	DU	

E = Escalate to the next higher dose
 S = Stay at the current dose
 D = De-escalate to the next lower dose
 DU = The current dose is unacceptably toxic
 Target toxicity rate = 30%
 Non-informative prior is used: $a=1$; $b=1$;
 $k1=1$; $k2=1.5$; $pow=1$ per {Ji, 2007 #55124}.

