5.2.4 Replacement of Subjects in DLT Evaluation Period

In order to determine safety, all subjects selected must meet the criteria for evaluability for Cycle 1. Subjects are considered non-evaluable and will be replaced if:

- They are enrolled but not treated
- They discontinue from the trial prior to completing all the safety evaluations for reasons other than treatment-related adverse events
- They receive less than 90% of the total MK-1966 or SD-101 in Cycle 1 (e.g., because the infusion had to be discontinued due to an infusion reaction) and did not experience a DLT

Non-evaluable subjects will not be counted toward the cohort total for DLT evaluation.

If a subject experiences a DLT in Cycle 1, trial treatment may be discontinued following discussion between the sponsor and Investigator. However, if the subject is deriving clinical benefit from the trial treatment, the subject may be allowed to continue after discussion between the sponsor and the Investigator.

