 - Subjects should receive full supportive care to treat injection site reactions.. Injection-site reactions are expected to spontaneously subside. Local reactions

are to be treated at the discretion of the treating physician. The site is not to be injected if local pain, tenderness, or swelling persists from a previous injection or other cause; the injection may be postponed until the symptoms have resolved. The injection may be skipped, following agreement with the Medical Monitor.

- **Pneumonitis:** For **Grade 2 events**, treat with systemic corticosteroids. When symptoms improve to Grade 1 or less, steroid taper should be started and continued over no less than 4 weeks.
 - For **Grade 3-4 events**, immediately treat with intravenous steroids. Administer additional anti-inflammatory measures, as needed.
 - Add prophylactic antibiotics for opportunistic infections in the case of prolonged steroid administration.
- **Renal Failure or Nephritis:**
 - For Grade 2 events, treat with corticosteroids
 - For Grade 3-4 events, treat with systemic corticosteroids
 - When symptoms improve to Grade 1 or less, steroid taper should be started and continued over no less than 4 weeks.
- **Type 1 Diabetes Mellitus** (if new onset, including diabetic ketoacidosis) or \geq Grade 3 hyperglycemia, if associated with ketosis (ketonuria) or metabolic acidosis (diabetic ketoacidosis)
 - Insulin replacement therapy is recommended for Type 1 diabetes mellitus and for Grade 3-4 hyperglycemia associated with metabolic acidosis or ketonuria.
 - Evaluate patients with serum glucose and a metabolic panel, urine ketones, glycosylated hemoglobin, and C-peptide.

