8.6.2 Statistical Methods for Safety Analyses

Safety and tolerability will be assessed by clinical review of all relevant parameters including AEs, SAEs, laboratory tests, vital signs, ECG measurements and physical examinations.

DLTs will be listed. DLTs and adverse experiences will be summarized as counts and frequencies for MK-1966 in combination with SD-101 dose level that had at least three subjects treated and listed for other dose levels. The estimate of the DLT rate among subjects treated with the RPTD and the 80% Bayesian probability interval with non-informative prior for the estimate will be provided. Laboratory assessments, vital signs, and other safety endpoints will be summarized as appropriate.

In addition, the broad clinical and laboratory AE categories consisting of the percentage of subjects with any AE, a drug related AE, a serious AE, an AE which is both drug-related and serious, and who discontinued due to an AE will be summarized for dose levels with at least 3 subjects treated and listed for other doses. Percentages of subjects in these categories among subjects treated with RPTD and 80% confidence intervals for the estimated percentages calculated using the Clopper-Pearson method will be provided.

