8.6.4 Precision of the DLT rate at RPTD

Since the TPI approach will be used during the dose confirmation/expansion parts B and C, the estimated DLT rate, and its 80% Bayesian Probability Interval (PI) will be calculated from the posterior distribution of the DLT rate at RPTD using the model specified in the TPI approach. If 20 subjects are finally dosed at RPTD during the dose confirmation/expansion stage, the estimated DLT rate and its 80% PI should be similar to one of the rows in [Table 12](#).

Table 12 Precision of the Estimated DLT rates at RPTD

Number of Subjects dosed at RPTD	Number of DLT Events	Estimated DLT Rate	Lower Bound of 80% PI	Upper Bound of 80% PI
20	2	0.10	0.036	0.206
20	3	0.15	0.069	0.267
20	4	0.20	0.105	0.325
20	5	0.25	0.144	0.381
20	6	0.30	0.185	0.435
20	7	0.35	0.228	0.487

Assume non-informative prior distribution of DLT.

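### The SAP's DLT evaluation set (8.5.1) omits the 90% Cycle 1 dose condition of protocol 5.2.4, so under-dosed, replaced subjects without a DLT would count as non-events in the reported DLT rate

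*Combined protocol and SAP*

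**What the plan says.** Two sections define who counts for DLT evaluation.

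- **Protocol 5.2.4** lists the grounds for non-evaluability and replacement. One is "They receive less than 90% of the total MK-1966 or SD-101 in Cycle 1" when the subject did not have a DLT. It then states: "Non-evaluable subjects will not be counted toward the cohort total for DLT evaluation".
- **SAP 8.5.1** starts from APaT (at least one dose received) and says: "For DLT evaluation, APaT subjects that were observed for safety for 21 days after the first dose of assigned treatment", or with a DLT before that time, will be used. It has no exposure condition and does not refer to 5.2.4.

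The dose-confirmation rules in 5.2.1.2.2 use the protocol's notion of evaluability: "the number of subjects who are evaluable for DLT versus the number of subjects who developed a DLT will be continuously assessed".

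The reported result is set in 8.6.2: "The estimate of the DLT rate among subjects treated with the RPTD and the 80% Bayesian probability interval with non-informative prior" will be provided. Section 8.6.4 adds that this is "calculated from the posterior distribution of the DLT rate at RPTD using the model specified in the TPI approach" and that, if 20 subjects are finally dosed at the RPTD, "the estimated DLT rate and its 80% PI should be similar to one of the rows in" Table 12. Neither section restores the 90% condition.

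**The concern.** DLT is the primary endpoint (8.1, 8.4.2), and the DLT rate at the RPTD with its 80% interval is the main estimate reported for it. A programmer working from Section 8 would count as a full non-event a subject whom the protocol had already declared non-evaluable and replaced. The reported denominator could then include subjects who were left out when the dose was accepted.

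The error runs in one direction. Under-dosed subjects who do have a DLT are in both sets, so only non-events are added. The routes to under-dosing described below also start from tolerability problems, so adding these subjects makes the dose look somewhat safer. At stake is the accuracy of the reported rate. No hypothesis test depends on it.

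**Working it through.** **1. Can a subject be under-dosed in Cycle 1 without a DLT?** Yes, by two routes, both limited.

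- *Skipped SD-101 injection.* Section 5.7.1 says of a site with persisting local symptoms: "The injection may be skipped, following agreement with the Medical Monitor". Table 5 puts three SD-101 injections in the 21-day Cycle 1 (Days 1, 8, 15). With one injected lesion (all of Part A under 7.1.1.9.2, and Parts B and C when only one is chosen), one skip leaves 2/3 = 66.7% of the planned dose, below 90%. The same section also allows postponement, and an injection postponed but still given within Cycle 1 keeps the full dose.
- *Stopped MK-1966 infusion.* This is 5.2.4's own example. Grade 3 or 4 infusion reactions require permanent discontinuation (Tables 7 and 8). When drug-related, they are DLTs under 5.2.2 item 6 and count as events in both sets. A Grade 2 reaction that settles within an hour may be restarted at half rate and may still reach 90%. What remains is the Grade 2 reaction where the infusion is not restarted.

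**2. Reproduce Table 12.** Inputs: prior Beta(1,1) from the notes to Table 6; n = 20; x = number of DLTs.

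- Posterior: Beta(1 + x, 1 + n − x).
- Estimate: posterior mode = x/n.
- 80% interval: the shortest interval holding 80% of the posterior (highest density).

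| x | Estimate | Computed interval | Table 12 |
|---|---|---|---|
| 2 | 0.10 | 0.036–0.206 | 0.036–0.206 |
| 3 | 0.15 | 0.069–0.267 | 0.069–0.267 |
| 4 | 0.20 | 0.105–0.325 | 0.105–0.325 |
| 5 | 0.25 | 0.144–0.381 | 0.144–0.381 |
| 6 | 0.30 | 0.185–0.435 | 0.185–0.435 |
| 7 | 0.35 | 0.228–0.487 | 0.228–0.487 |

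All six rows match. Equal-tailed intervals do not: for x = 6 the same posterior gives 0.196–0.448.

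**3. Add u under-dosed subjects without a DLT.** The documents give no rate for these, so u is an assumption. Under 5.2.4 the set stays at n = 20. Under 8.5.1 as written it becomes n = 20 + u.

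| DLTs | u = 0 (5.2.4) | u = 1 | u = 2 | u = 3 |
|---|---|---|---|---|
| 2 | 0.100 (0.036–0.206) | 0.095 (0.034–0.197) | 0.091 (0.032–0.189) | 0.087 (0.031–0.181) |
| 6 | 0.300 (0.185–0.435) | 0.286 (0.175–0.416) | 0.273 (0.167–0.400) | 0.261 (0.159–0.384) |
| 7 | 0.350 (0.228–0.487) | 0.333 (0.216–0.467) | 0.318 (0.205–0.448) | 0.304 (0.195–0.431) |

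For zero DLTs the estimate stays at 0 and the upper bound is 1 − 0.2^(1/(n+1)): 0.074, 0.071, 0.068 and 0.065 for n = 20, 21, 22 and 23.

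**4. Direction and size.** Since x/(n + u) < x/n for any x ≥ 1 and u ≥ 1, the rate always falls when there is at least one DLT. For six DLTs and u = 2 the shift is 0.300 − 0.273 = 0.027, against an interval width of 0.435 − 0.185 = 0.250.

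**5. Larger denominator.** Section 8.6.3.5 plans 20 subjects at the RPTD in Part B and 20 in Part C. If the report pools about 40, two added non-events take 12/40 = 0.300 to 12/42 = 0.286, a shift of 1.4 points.

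**The case against.** **The sections can be read together.** They belong to one document and both speak of DLT evaluation, and 8.5.1 does not say that it overrides 5.2.4. A careful analyst might carry the 90% rule across. That is a fair reading, and nothing suggests that 8.5.1 was meant to reverse 5.2.4. But 8.5.1 is written as a complete definition, and the denominator of the primary endpoint should not rest on inference.

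**The routes are narrow.** This stands in part. Criterion 6 of 5.2.2 turns Cycle 1 discontinuations for drug-related events into DLTs, and postponed injections and restarted infusions may still reach 90%. Skipped injections and unrestarted Grade 2 infusions remain.

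**A larger denominator need not signal this problem.** This also stands. A reader might infer from Table 12 that the reporting and confirmation counts must both be 20. The documents do not support that: the reference to Table 12 is conditional on 20 subjects, and 8.6.3.5 plans 20 + 20 at the RPTD while counting only 20 of them towards the MTD.

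**A lower rate is not necessarily a wrong one.** The 5.2.4 set keeps under-dosed subjects with a DLT and drops those without, which pushes its rate up. An as-treated rate with 21 days of follow-up is defensible as a supplementary figure. It is still a different quantity from the one on which the dose is accepted, and the plan does not present it as such.

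**Both counts could be recovered** from the DLT listings and dosing records. True, but in an open-label trial the choice between them should be made beforehand.

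**Conclusion.** The point holds as a conflict between two stated rules for the same purpose. As written, 8.5.1 counts replaced, under-dosed subjects without a DLT as non-events. That lowers the reported DLT rate at the RPTD whenever there is at least one DLT, and lowers only the upper bound when there are none.

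The size is modest: with one to three such subjects added to 20, about 1.4 to 3.9 points at six DLTs (0.300 to 0.286, 0.273 or 0.261), and about half as much for two subjects if some 40 are pooled. This rests on an assumed number of under-dosed subjects who complete 21 days of observation. If there are none, nothing changes.

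A reader might infer that escalation or dose confirmation is compromised. The documents do not support that, because those decisions use evaluable subjects under 5.2.4. Nor do they support the view that poorly tolerating subjects in general are counted as non-events, because those who discontinue treatment in Cycle 1 for a drug-related event are DLTs in either set. The correction should be made because it settles the primary-endpoint denominator at almost no cost.

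**What to change.** Replace the DLT sentence in 8.5.1 with:

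*For DLT evaluation, APaT subjects evaluable under Section 5.2.4 will be used: those who had a DLT in Cycle 1 (Section 5.2.2), or who received at least 90% of planned MK-1966 and at least 90% of planned SD-101 in Cycle 1 and completed the 21-day safety observation.*

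State in 8.6.2 and 8.6.4 that the DLT rate and its 80% interval are computed on this set. Keep under-dosed subjects in APaT for all adverse event summaries.

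The cost is one replaced sentence and a pointer in two others. It adds no subjects or visits, and no new exclusion, because 5.2.4 already excludes and replaces these subjects. The dose-modification rules in Table 7 need no change.
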